**Title: Evaluation of WIRION™ EPS in Lower Extremities Arteries**

Document No. CL-003

Version 2.2

Page 4 of 4

	
100 (68.5%) of the originally planned subjects have reached the 30-day follow-up. Using an Exact Binomial Test and under the following assumptions:
 
Alpha (one-sided) = 0.025 <math>\beta</math>= 0.20 PE= 10.7% Performance goal= 19.26%
 
An estimated 145 evaluable subjects will be required for 80% power if the study reaches the final analysis. With an anticipated combined loss-to-follow-up of up to 5%, 153 patients will be enrolled in the study.
 
An interim analysis will be performed when 100 subjects (approximately 68.5% of the 145 evaluable subjects) have completed the study; two potential options will be pursued:
 
The study will be stopped for efficacy if the primary null hypothesis is rejected at one sided alpha = 0.0068 based on the Lan-DeMets alpha spending function with O'Brien - Fleming boundaries.
 
If based on the interim analysis the primary null hypothesis cannot be rejected, then the trial will continue to a total sample size of 153 enrolled subjects (i.e., 145 evaluable subjects). This test will be conducted at one-sided alpha = 0.0229, in order to control the overall Type I error at 2.5%.
 
Study success is defined as rejecting the null hypothesis.

Duration of Study	The estimated study duration is ten months, including a recruitment phase and follow up period of 30±7 days

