**Title: Evaluation of WIRION™ EPS in Lower Extremities Arteries**

Document No. CL-003

Version 2.2

Page 2 of 4

	
 
5) Has perforation, dissection, or other injury of the access or target vessel requiring additional stenting or surgical intervention before enrollment
 
6) Subject is enrolled in another drug or device study protocol that has not reached its primary endpoint (participating in registry studies is not excluded)
 
7) Life expectancy less than 12 months
 
8) Known severe renal insufficiency (eGFR <30 ml/min/1.72m^2).
 
9) ≤1-vessel tibial run-off status
 

Number of subjects:	Up to 153 with an interim analysis after 100 subjects
Clinical sites:	Up to 10 sites; up to 1/3 of the study patients at OUS sites
Investigational Product:	WIRION™ Embolic Protection System (Gardia Medical Ltd.)
Primary end point	
Freedom from major adverse events (MAE) to 30 days post procedure.
 
MAE defined as a serious adverse event that results in death, acute myocardial infarction, thrombosis, pseudo-aneurysm, dissection (grade C or greater) or clinical perforation at the filter location, distal embolism (clinically relevant), unplanned amputation, or clinically-driven target vessel revascularization (TVR), through 30 days post-procedure, as adjudicated by the Clinical Events Committee (CEC).

Secondary end points	
 
• Device success Defined as: 
 
- A successful delivery and deployment of WIRION™ distal to the intervention site without complications, AND
 
- Successful retrieval of WIRION™ following completion of the stenting procedure, without complications
 
 
 
• Clinical success Defined as: Device success with freedom from procedure related serious adverse events ascribed to the WIRION
 
• Technical success Defined as: Freedom from device malfunctioning causing the procedure to be aborted
 
• Percent of filters with visible debris
 

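### Does it matter that the printed interim fraction (68.5%) and interim level (0.0068) fit 100/146 and not 100/145?

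*Combined protocol and SAP*

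**What the plan says.** The design has at most two stages, with boundaries from a Lan-DeMets spending function of O'Brien-Fleming type and an exact binomial test.

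The timing of the interim look is worded three ways:

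- Number of subjects row: "Up to 153 with an interim analysis after 100 subjects".
- Statistical Considerations, first mention: "100 (68.5%) of the originally planned subjects have reached the 30-day follow-up".
- Statistical Considerations, second mention: "100 subjects (approximately 68.5% of the 145 evaluable subjects) have completed the study".

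The stopping rule is that the null hypothesis be "rejected at one sided alpha = 0.0068 based on the Lan-DeMets alpha spending function". If the trial continues, the final test is at one-sided 0.0229. The final count is 145 evaluable subjects, and 153 are enrolled to allow for loss to follow-up of up to 5%. The synopsis gives no separate rule for an interim count other than 100.

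**The concern.** Two things look wrong.

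First, the fraction and the level cannot be derived from the stated 145. They come from 146, a number that appears nowhere in the document. An interim boundary computed for the wrong maximum sample size could, in principle, spend the wrong amount of alpha.

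Second, the plan prints a fixed level and also names a spending function, whose purpose is to adapt the level to the information actually available. If the number analysed is not 100, the two can give different cutoffs. Rejection at the interim counts as study success, and events in an open-label single-arm study are visible as they accrue. A choice left open until the count is known could therefore look opportunistic.

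**Working it through.** **Inputs** (all from Statistical Considerations): "Alpha (one-sided) = 0.025"; "PE= 10.7% Performance goal= 19.26" (per cent); "An estimated 145 evaluable subjects will be required for 80% power"; interim at 100; levels 0.0068 and 0.0229.

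**1. The plan's interim level.** The spend at fraction t is 2 − 2Φ(z₀.₉₈₇₅/√t), with z₀.₉₈₇₅ = 2.2414.

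- t = 100/146 = 0.6849: 2.2414/√t = 2.708, spend 0.00676, which rounds to the printed 0.0068.
- t = 100/145 = 0.6897: 2.2414/√t = 2.699, spend 0.00695, which rounds to 0.0070.
- t = 100/153 = 0.6536: spend 0.0056, so enrolled subjects are not the denominator either.

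A possible source of 146 (inference, not stated) is the one-stage normal-approximation sample size at one-sided 0.025:
[(1.960·√(0.1926·0.8074) + 0.8416·√(0.107·0.893)) / 0.0856]² = 145.65, rounded up to 146. The enrolment figure follows 145: 145/0.95 = 152.6, giving 153, whereas 146/0.95 = 153.7 would give 154.

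**2. The final level.** With the two test statistics correlated √t, the level that brings the total to 0.025 is 0.02293 for 146 and 0.02288 for 145. Both round to the printed 0.0229. Using 0.0068 and 0.0229 at t = 100/145, the normal-theory total is 0.02495, below 0.025.

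**3. The decision at 100 evaluable.** At an MAE rate of 19.26%, P(X ≤ 9 | 100) = 0.0039 and P(X ≤ 10 | 100) = 0.0092. Both 0.0068 and 0.0070 lie between them, so the rule is 9 or fewer MAEs either way. At the end, P(X ≤ 18 | 145) = 0.0196 and P(X ≤ 19 | 145) = 0.0336, so the final rule is 18 or fewer. The overall exact type I error is 0.0207 and two-stage power at 10.7% is 79.6%.

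**4. Other interim counts.** Assumption: the evaluable count at the look may fall between 95 (5% loss from 100 enrolled) and 110 (a later data cut). The final rule is 18 or fewer of 145 throughout. The two readings give the same cutoff at every count except these:

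| Interim n | Reading | Cutoff | Type I error | Power | P(stop) at 10.7% |
|---|---|---|---|---|---|
| 96 | fixed 0.0068 | ≤9 | 2.22% | 79.8% | 41.6% |
| 96 | function (0.0059) | ≤8 | 2.03% | 79.4% | 28.9% |
| 102 | fixed 0.0068 | ≤9 | 2.03% | 79.5% | 33.8% |
| 102 | function (0.0075) | ≤10 | 2.22% | 79.9% | 46.4% |
| 107 | fixed 0.0068 | ≤10 | 2.05% | 79.5% | 39.8% |
| 107 | function (0.0091) | ≤11 | 2.28% | 80.1% | 52.3% |
| 108 | fixed 0.0068 | ≤10 | 2.03% | 79.5% | 38.6% |
| 108 | function (0.0094) | ≤11 | 2.22% | 79.9% | 51.0% |
| 109 | fixed 0.0068 | ≤10 | 2.02% | 79.4% | 37.3% |
| 109 | function (0.0097) | ≤11 | 2.18% | 79.8% | 49.6% |

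From 97 to 101, the counts nearest the planned look, the two readings agree.

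**The case for a change.** The best argument for a change is that the arithmetic is plainly wrong. The first mention of 68.5% has no softening word, and 0.0068 follows the same wrong denominator to four decimals. None of the three trigger wordings says that the 100 must be evaluable, although the final count is defined that way. At 96 or 102 evaluable, one event count, with probability 12.6% at the assumed MAE rate, would stop the trial under one reading and not the other. A sentence would settle it.

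The arithmetic part stands as a clerical point. The rest is weaker than it looks. The stopping rule gives 0.0068 as the level of the test and names the spending function as its source, so a plain reading leaves little doubt about what to apply. Both descriptions in Statistical Considerations count subjects who have reached or finished follow-up, and one expresses the 100 as a share of the evaluable total. A count of 96 needs the brief summary row to mean 100 enrolled, with a loss allowance that the plan applies only to total enrolment. A count of 102 needs a data cut later than the stated trigger.

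Nor is an added rule free of trouble. Fixing the look at the first 100 evaluable subjects makes a provision for other counts nearly redundant. Recomputing only the interim level would leave the final level undefined in exactly the case the rule is meant to cover.

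**Conclusion.** No change follows. The printed fraction is half a percentage point off, and the printed level errs on the strict side for 145. At the planned 100 evaluable subjects the interim rule, the final level, type I error (2.07%) and power (79.6%) are the same with either denominator. The missing provision for other counts is a gap that analysts fill sensibly, by using the printed level or by re-evaluating the function. Over the assumed range of 95 to 110, both keep type I error at 2.02% to 2.28% and power at 79.4% to 80.1%. What the choice can alter, at five isolated counts, is mainly whether success is declared at the interim or at the end.

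This rests on the design values of 10.7% and 19.26%, on 145 evaluable subjects at the final analysis, and on the synopsis being the only text available. If the text is reissued for another reason, the percentage can be tidied or its 146 basis stated; the result does not depend on it.

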Study Population:	
Both male and female subjects who meet all the eligibility criteria and give written informed consent will be enrolled in the study.
 
Inclusion Criteria
 
 
1) Subject is at least 18 years of age
 
2) Subject or authorized representative, signed a written Informed Consent form to participate in the study, prior to any study related procedures
 
3) Subject is willing to comply with the protocol requirements and return to the treatment center for all required clinical evaluations
 
4) Rutherford classification 2-4
 
5) Has moderate to severe calcification visualized on angiogram in the femoropopliteal arteries
 
6) Planned atherectomy of the native femoropopliteal arteries
 
7) Reference vessel diameter for intended filter location must be visually estimated to be ≥3.5mm and ≤6.0mm
 
8) An adequate “landing zone” for placement of the WIRION™ device distal to the target lesion of at least 30mm
 
9) A female subject is eligible if not of child bearing potential or has a negative pregnancy test within the previous 7 days and agrees to remain on birth control throughout the study
 
 
Exclusion Criteria
 
 
1) Any planned surgical or endovascular intervention within 30 days before or after the index procedure
 
2) A lesion deemed not accessible by the WIRION™ EPS
 
3) Inability to take aspirin or ADP receptor antagonists
 
4) History of bleeding diathesis or coagulopathy or will refuse blood transfusion if deemed necessary
 

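### The interim rule continues to 153 subjects even after 20 or more MAEs in 100, when study success is already impossible

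*Combined protocol and SAP*

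**What the plan says.** The Number of subjects row of the synopsis reads "Up to 153 with an interim analysis after 100 subjects". Under Statistical Considerations, the interim analysis takes place when 100 subjects "have completed the study; two potential options will be pursued". The first option is to stop for efficacy if the null hypothesis (MAE rate at or above 19.26%) is rejected at one-sided 0.0068. The second is that if "the primary null hypothesis cannot be rejected, then the trial will continue to a total sample size of 153 enrolled subjects", taken as 145 evaluable, with a final test at one-sided 0.0229.

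There is one success criterion: "Study success is defined as rejecting the null hypothesis". The synopsis gives no futility or safety branch, and it does not say whether enrolment pauses while the interim events are adjudicated.

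**The concern.** The second option covers every interim count that does not reject, however high. Events already observed stay in the final count, so above some number the final test cannot reject whatever happens in the remaining subjects. The plan still directs the trial to go on.

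This matters because the primary endpoint is a safety composite that includes death, myocardial infarction and unplanned amputation. Followed literally, the rule can enrol more subjects with an investigational filter after the primary objective is out of reach. These subjects would already be having an atherectomy (inclusion criterion 6), so the added exposure is to the filter and the study procedures. What is at stake is exposure and efficiency, not the validity of the test. Twenty events in a single arm would not by themselves show that the filter caused harm.

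**Working it through.** **Inputs (Statistical Considerations).** Exact binomial test; null rate p0 = 0.1926; expected rate p1 = 0.107; overall one-sided alpha 0.025; interim at 100; nominal levels 0.0068 and 0.0229; 145 evaluable; 153 enrolled with up to 5% loss. The working assumes that the 100 interim subjects and their adjudicated events carry into the final analysis.

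**1. The plan's own figures.** 145 / 0.95 = 152.6, rounded up to 153. Lan-DeMets spending of O'Brien-Fleming type at fraction 0.685 gives 0.0068 and 0.0229, as stated. (100/145 is 0.690, which would give 0.0070 at interim; the event limits below do not change.) Exact two-stage power at 145 is 0.3628 (interim) + 0.4327 (final) = 0.7955, and type I error is 0.0039 + 0.0168 = 0.0207. The design reproduces.

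**2. Event limits.** The limit is the largest c with P(X ≤ c | n, 0.1926) at or below the nominal level.

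| Analysis | Level | Limit c | P(X ≤ c) | P(X ≤ c + 1) |
|---|---|---|---|---|
| Interim, n = 100 | 0.0068 | 9 | 0.0039 | 0.0092 |
| Final, n = 145 | 0.0229 | 18 | 0.0196 | 0.0336 |
| Final, n = 150 | 0.0229 | 19 | 0.0219 | 0.0369 |
| Final, n = 153 | 0.0229 | 19 | 0.0168 | 0.0288 |

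The final limit is 18 for n = 144 to 149 and 19 for n = 150 to 153. Every interim count from 10 upward therefore goes to continuation.

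**3. Chance of final success from x events at interim.** This is P(Y ≤ c − x), with Y binomial on n − 100 subjects. It is exactly 0 once x exceeds c, whatever the future rate. At p1 = 0.107:

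| x in 100 | n = 145 | n = 150 | n = 153 |
|---|---|---|---|
| 18 | 0.893^45 = 0.0061 | 0.0244 | 0.0183 |
| 19 | 0 | 0.893^50 = 0.0035 | 0.893^53 = 0.0025 |
| 20 or more | 0 | 0 | 0 |

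So 20 rules out success at every size up to 153, and 19 already does so at the planned 145.

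**4. How often this arises.**

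| True MAE rate | P(≥ 19 of 100) | P(≥ 20 of 100) |
|---|---|---|
| 10.7% | 0.9% | 0.4% |
| 15% | 16.3% | 10.7% |
| 19.26% | 56.6% | 46.5% |
| 25% | 93.7% | 90.0% |

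**5. Effect of stopping at 20.** Power and type I error are the same with and without the stop: 0.7955 and 0.0207 at 145; 0.8232 and 0.0231 at 150; 0.8007 and 0.0183 at 153. A stop at 19 leaves 145 unchanged and lowers power by less than 0.002 percentage points at 150 to 153.

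**6. Subjects spared.** About 100 / 0.95 = 105.3 must be enrolled to give 100 evaluable, so at most 153 − 105.3 = 47.7 remain. Without a pause, the number spared is max(0, 47.7 − rate × (30 to 37 days in months + lag)). The synopsis gives no accrual rate. The ten-month Duration of Study implies about 153 / 9.0 = 17.0 to 153 / 8.8 = 17.4 per month; 15 to 25 is an assumed range.

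| Rate per month | No lag | One-month lag | Two-month lag |
|---|---|---|---|
| 15 | 30–33 | 15–18 | 0–3 |
| 17 | 27–31 | 10–14 | 0 |
| 20 | 23–28 | 3–8 | 0 |
| 25 | 17–23 | 0 | 0 |

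**The case against.** An efficacy-only group sequential design is complete and legitimate. Nothing in the rule is contradictory or miscalculated, so this is a preference rather than a defect. That stands, and it is why the point is only one to consider.

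The expected benefit is also small. At 10.7% it is about 0.0043 × 48 = 0.2 subjects, even with a pause. At 17 per month with a one-month lag it is 0.1065 × 10 to 14, or about 1.1 to 1.5, at a true rate of 15%, and 0.4654 × 10 to 14, or about 4.7 to 6.5, at the performance goal. Because events must be adjudicated by committee, the no-lag figures are optimistic, and without a pause the rule may spare nobody. This stands too. It is the reason to settle the pause in the same edit.

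Continuing also has value: the objective covers safety and performance, and the secondary endpoints gain from the full sample. A non-binding rule leaves that choice open. A threshold at the point of no return also lets near-hopeless counts continue, such as 18 at 145 (0.6%). That is true, but any lower threshold starts to cost power.

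Finally, the document is a four-page synopsis, and a fuller protocol or charter may hold a further rule. The point is limited to the synopsis wording, which as it stands allows only two outcomes.

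**Conclusion.** The point holds as a low-cost improvement, not an error. As worded, the rule sends 20 or more MAEs in 100 to continued enrolment although the chance of meeting the only success criterion is exactly zero at any final size up to 153. At the planned 145, the same is true from 19. The situation is rare if the device performs as assumed (0.4%) and close to even odds if the true rate equals the performance goal (46.5%).

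The limits rest only on the stated test and levels and on the interim events staying in the final set. The number spared is uncertain: at most about 48 with a pause near 105 enrolled, and otherwise dependent on accrual and adjudication lag, possibly 0. Power, type I error and the nominal levels are not affected.

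**What to change.** In Statistical Considerations, change the number of interim options from two to three and add:

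> If 20 or more of the 100 interim subjects (including any who died before day 30) have an adjudicated MAE, the primary objective can no longer be met and stopping enrolment is recommended. This recommendation is non-binding: if the sponsor continues, for example for precision of the MAE rate and secondary endpoints, the reason is documented and the final test at 0.0229 is unchanged.

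The mention of early deaths is needed because death is an MAE, yet such a subject might be read as not having completed the study. Open the continuation sentence with *Otherwise*, and state whether enrolment pauses during interim adjudication. If the final analysis is fixed at 145 evaluable subjects, 19 can replace 20. If a fuller protocol or charter already has such a rule, reconcile the synopsis with it.

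The cost is two sentences, two edited phrases and the statement on pausing. No power or alpha is spent, and 0.0068 and 0.0229 stay. The downside if the trial stops is less precision: the exact 95% interval is 12.7% to 29.2% at 20/100, against 13.8% to 27.4% at 29/145, with a similar loss for the secondary endpoints.
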